### **12.10.6. Detailed Dose Escalation /De-escalation Scheme for BLRM Design for Sasanlimab + Encorafenib + Binimetinib**

This section provides the details of the statistical model, the derivation of prior distributions from historical data, the results of the Bayesian analyses and respective dosing decisions for some hypothetical data scenarios, and a simulation study of the operating characteristics of the model for the encorafenib, binimetinib, and sasanlimab triplet combination.

#### **Statistical Model**

The statistical model for combination dose-DLT data comprises single-agent toxicity parts, and interaction parts. The single-agent toxicity parts allow the incorporation of single-agent toxicity data

#### **Single-Agent Parts**

Let  $\pi_1(d_1)$  be the risk of DLT for encorafenib given as a single agent at dose  $d_1$ ;  $\pi_2(d_2)$  be the risk of DLT for binimetinib given as a single agent at dose  $d_2$ ; and  $\pi_3(d_3)$  be the risk of DLT for sasanlimab given as a single agent at dose  $d_3$ . These single agent dose-DLT models are 2 parameter logistic regression models:

$$\text{encorafenib: } \text{logit}(\pi_1(d_1)) = \log(\alpha_1) + \beta_1 \log(d_1/d_1^*)$$

$$\text{binimetinib: } \text{logit}(\pi_2(d_2)) = \log(\alpha_2) + \beta_2 \log(d_2/d_2^*)$$

$$\text{sasanlimab: } \text{logit}(\pi_3(d_3)) = \log(\alpha_3) + \beta_3 \log(d_3/d_3^*)$$

where  $d_1^*=450$  mg,  $d_2^*=45$  mg, and  $d_3^*=300$  mg are used to scale the doses of encorafenib, binimetinib, and sasanlimab, respectively. Hence,  $\alpha_1$ ,  $\alpha_2$ , and  $\alpha_3$  (all  $>0$ ) are the single-agent odds of a DLT at  $d_1^*$  mg,  $d_2^*$  mg, and  $d_3^*$  mg, respectively; and  $\beta_1$ ,  $\beta_2$ , and  $\beta_3$  (all  $>0$ ) are the increase in the log-odds of a DLT by a unit increase in log-dose.

#### **Interaction Parts**

Under an assumption that there is no interaction, the risk of a DLT at dose  $d_1$  of encorafenib, dose  $d_2$  of binimetinib, and dose  $d_3$  of sasanlimab is:

$$\pi_{123}^0(d_1, d_2, d_3) = 1 - (1 - \pi_1(d_1))(1 - \pi_2(d_2))(1 - \pi_3(d_3))$$

To model the interaction between encorafenib, binimetinib, and sasanlimab, the following 4 odds multipliers are introduced.

$\eta_{12}$ : 2-way interaction between encorafenib and binimetinib

$\eta_{13}$ : 2-way interaction between encorafenib and sasanlimab

$\eta_{23}$ : 2-way interaction between binimetinib and sasanlimab

$\eta_{123}$ : 3-way interaction between encorafenib, binimetinib, and sasanlimab

The risk of DLT for combination dose  $(d_1, d_2, d_3)$  is then given by:

$$\begin{aligned} \text{odds}(\pi_{123}(d_1, d_2, d_3)) &= g(\eta_{12}, \eta_{13}, \eta_{23}, \eta_{123}) \times \text{odds}(\pi_{123}^0(d_1, d_2, d_3)) \\ g(\eta_{12}, \eta_{13}, \eta_{23}, \eta_{123}) &= \exp(\eta_{12} \times d_1/d_1^* \times d_2/d_2^*) \\ &\quad \times \exp(\eta_{13} \times d_1/d_1^* \times d_3/d_3^*) \\ &\quad \times \exp(\eta_{23} \times d_2/d_2^* \times d_3/d_3^*) \\ &\quad \times \exp(\eta_{123} \times d_1/d_1^* \times d_2/d_2^* \times d_3/d_3^*) \end{aligned}$$

where  $\text{odds}(\pi) = \pi/(1 - \pi)$ ;  $\eta_{ij}$  is the log-odds ratio between the interaction and no interaction model at the reference doses of drug i and j and a zero dose of the third drug. For example,  $\eta_{23}$  is the log-odds ratio between the interaction and no interaction model at encorafenib = 0 mg, binimetinib = 45 mg and sasanlimab = 300 mg. Therefore,  $\eta_{12} + \eta_{13} + \eta_{23} + \eta_{123}$  is the log-odds ratio between the interaction and no interaction model at the reference doses for all 3 drugs. Here  $\eta = 0$  corresponds to no interaction, with  $\eta > 0$  and  $\eta < 0$  representing synergistic and antagonistic toxicity, respectively.

### **Inclusion of the Doublet Data**

Based on the preliminary data from the Phase 1b part of study CMEK162X2110, a total 47 participants were enrolled at the starting dose level of 45 mg for binimetinib in combination with escalating doses of encorafenib (ranging from 50 mg to 800 mg). Forty-four (44) participants were DLT-evaluable. This information from study CMEK162X2110 was incorporated in the assessment of prior distribution of DLT, starting dose, data scenarios, and simulations of triplet via a direct down-weighting approach. The weight was calculated using the formula below assuming moderate heterogeneity between the populations included in the binimetinib + encorafenib doublet and triplet in terms of DLT;

$$w = \frac{1}{1 + \frac{2\tau^2}{\sigma^2} N}$$

where, N= Total number of participants enrolled in the CMEK162X2110 (N=44)  
 $\sigma$  = population standard deviation ( $\sigma = 2$ )

$\tau$  = heterogeneity between populations in the CMEK162X2110 and current trial ( $\tau = 0.25$ )

### **Prior Specifications**

The Bayesian approach requires the specification of prior distributions for all model parameters, which include the single agent parameters  $\log(\alpha_1)$ ,  $\log(\beta_1)$  for encorafenib,  $\log(\alpha_2)$ ,  $\log(\beta_2)$  for binimetinib,  $\log(\alpha_3)$ ,  $\log(\beta_3)$  for sasanlimab, and the interaction

parameters  $\eta = (\eta_{12}, \eta_{13}, \eta_{23}, \eta_{123})$ . A meta-analytic-predictive (MAP) approach was used to derive the prior distribution for the single-agent model parameters.

### **Prior Distribution for the Logistic Parameters for Single Agent**

This section illustrates the derivation of prior distributions for single agent model parameters ( $\log(\alpha_s)$ ,  $\log(\beta_s)$ )’s using the available single agent dose-DLT information via a MAP approach.

### **Description of the Meta-Analytic-Predictive Approach**

The aim of the MAP approach is to derive a prior distribution for the logistic parameters ( $\log(\alpha^*)$ ,  $\log(\beta^*)$ ) of the new trial using DLT data from historical studies. Let  $r_{ds}$  and  $n_{ds}$  be the number of participants with a DLT, and the total number of participants at dose  $d$  in historical trial  $s$  ( $s = 1, \dots, \langle S \rangle$ ). The corresponding probability of a DLT is  $\pi_{ds}$ . The model specifications are as follows:

$$r_{ds} \mid \pi_{ds} \sim \text{Binomial}(\pi_{ds}, n_{ds})$$

$$\text{logit}(\pi_{ds}) = \log(\alpha_s) + \beta_s \log(d/d^*)$$

$$(\log(\alpha_s), \log(\beta_s)) \mid \mu, \psi_{g(s)} \sim \text{Bivariate Normal (BVN)}(\mu, \psi_{g(s)}), \quad s = 1, \dots, \langle S \rangle$$

$$(\log(\alpha^*), \log(\beta^*)) \mid \mu, \psi_{g(*)} \sim \text{BVN}(\mu, \psi_{g(*)})$$

The historical trials are partitioned into  $\langle G \rangle$  exchangeability groups, with the exchangeability group membership of historical trial  $s$  being represented by  $g(s)$ . The new trial is assigned to exchangeability group  $g(*)$ . The parameter  $\mu = (\mu_1, \mu_2)$  is the mean for the logistic parameters, and  $\psi_g$  is the between-trial covariance matrix for exchangeability group  $g = 1, \dots, \langle G \rangle$ . Covariance matrix  $\psi_g$  is defined by the standard deviations ( $t_{g1}, t_{g2}$ ), and correlation  $r$  (a common value for  $r$  is used across all groups). The parameters  $t_{g1}$  and  $t_{g2}$  quantify the degree of between trial heterogeneity for exchangeability group  $g$ . With different prior distributions for the parameter sets ( $t_{g1}, t_{g2}$ ) it is possible to allow for differential discounting for the historical strata. In this way the quality and relevance of historical data can be accounted for in the meta-analysis. The following priors will be used for these parameters:

normal priors for  $\mu_1$  and  $\mu_2$ ,

log-normal priors for  $t_{g1}$  and  $t_{g2}$ , and

uniform prior for  $r$ .

The MAP prior for single-agent model parameters in the new trial,  $(\log(\alpha^*), \log(\beta^*))$ , is the predictive distribution

$$(\log(\alpha^*), \log(\beta^*)) \mid (r_{ds}, n_{ds} : s = 1, \dots, \langle S \rangle)$$

Since the predictive distribution is not available analytically, the Markov chain Monte Carlo (MCMC) method is used to simulate values from this distribution. This is implemented using Just Another Gibbs Sampler (JAGS) version 4.8.

### **Single-Agent Encorafenib**

Dose-DLT data from the encorafenib IB (Edition 10) from Study CLGX818X2101 as presented in Table 12 are used to derive the prior of the single agent logistic parameters for encorafenib.

**Table 12. Historical Dose Limiting Toxicity data from study CLGX818X2101**

Encorafenib Dose (mg; QD)	Number of Participants	Number of Participants with DLTs
50	4	0
100	9	1
150	6	0
200	3	0
300	5 (escalation); 14 (expansion)	1(escalation); 2 (expansion)
450	6 (escalation); 27 (expansion)	0 (escalation); 9(expansion)
550	4	1
700	2	2

Weakly informative normal priors are assumed for  $\mu_{1e}$  and  $\mu_{2e}$ , with means corresponding to a 50% chance of DLT at encorafenib = 450 mg and a doubling in dose leading to a doubling in the odds of the risk of a DLT, respectively. Priors for  $t_{1e}$  and  $t_{2te}$  are assigned such that (1) their medians correspond to moderate to large between trial heterogeneity, and (2) their uncertainty (95% prior interval) cover plausible between-trial standard deviations (Table 13).

**Table 13. Prior Distributions for the Parameters of the MAP Model Used to Derive the Prior for the Single-Agent Encorafenib Model Parameters**

Parameter	Prior Distribution
$\mu_{1e}$	N (mean = 0, sd = 2)
$\mu_{2e}$	N (mean = 0, sd = 1)
$t_{1e}$	log-normal (mean = log (0.50), sd = log (2)/1.96)
$t_{2e}$	log-normal (mean = log (0.25), sd = log (2)/1.96)
$r_e$	Uniform (-1,1)

### **Single-Agent Binimetinib**

Dose-DLT data in the binimetinib IB (Edition 16) from studies ARRAY-162-111 and CMEK162X1101 as presented in Table 14 are used to derive the prior of the single agent logistic parameters for binimetinib.

**Table 14. Historical Dose Limiting Toxicity Data from Study Array-162-111 and Study CMEK162X1101**

Binimetinib dose (mg BID)	Study Array-162-111		Study CMEK162X1101	
	Number of Participants	Number of Participants with DLTs	Number of Participants	Number of Participants with DLTs
30	3	0	6	0
45	43	2	15	2
60	40	2		
80	3	2		

Weakly informative normal priors are assumed for  $\mu_{1b}$  and  $\mu_{2b}$ , with means corresponding to a 50% chance of DLT at binimetinib = 45 mg, and a doubling in dose leading to a doubling in the odds of the risk of a DLT, respectively. The priors for between-trial heterogeneity parameters are set in the following way:

- Priors for  $t_{11b}$  and  $t_{12b}$  (ARRAY-162-111) are assigned such that (1) their medians correspond to moderate between-trial heterogeneity, and (2) their uncertainty (95% prior interval) cover plausible between-trial standard deviations.
- Priors for  $t_{21b}$  and  $t_{22b}$  (CMEK162X1101) are assigned such that (1) their medians correspond to large between-trial heterogeneity, and (2) their uncertainty (95% prior interval) cover plausible between-trial standard deviations.

Study ARRAY-162-111 is a Phase 1 study conducted in advanced or metastatic cancer participants the US. Study CMEK162X1101 is a study in Japanese participants with advanced solid tumors whose disease has progressed despite standard therapy or for whom no standard therapy exists. The participant population in Study CMEK162X1101 is less similar to Study B8011011 and hence large between trial heterogeneity is assumed.

**Table 15. Prior Distributions for the Parameters of the MAP Model Used to Derive the Prior for the Single-Agent Binimetinib Model Parameters**

Parameter	Prior Distribution
$\mu_{1b}$	N (mean = 0, sd = 2)
$\mu_{2b}$	N (mean = 0, sd=1)
$t_{11b}$	log-normal (mean = log (0.25), sd = log (2)/1.96)
$t_{12b}$	log-normal (mean = log (0.125), sd = log (2)/1.96)
$t_{21b}$	log-normal (mean = log (1), sd = log (2)/1.96)
$t_{22b}$	log-normal (mean = log (0.5), sd = log (2)/1.96)
$r_b$	Uniform (-1,1)

**Table 15. Prior Distributions for the Parameters of the MAP Model Used to Derive the Prior for the Single-Agent Binimetinib Model Parameters**

Parameter	Prior Distribution
-----------	--------------------

$(t_{11b}, t_{12b})$  = the degree of between trial heterogeneity for Study ARRAY-162-111;  $(t_{21b}, t_{22b})$  = the degree of between-trial heterogeneity for Study CMEK162X1101.

**Single Agent PF-06801591**

Dose-DLT data from study B8011001 presented in Table 16 are used to derive the prior of the single agent logistic parameters for sasanlimab.

**Table 16. Historical Dose Limiting Toxicity data from Study B8011001**

Sasanlimab Dose (mg/once per cycle)	Number of Participants	Number of Participants with DLTs
300	15	0

Weakly informative normal priors are assumed for  $\mu_{1p}$  and  $\mu_{2p}$ , with means corresponding to a 50% chance of DLT at sasanlimab = 300mg, and a doubling in dose leading to a doubling in the odds of the risk of a DLT, respectively. Priors for  $t_{1p}$  and  $t_{2p}$  are assigned such that (1) their medians correspond to moderate between trial heterogeneity, and (2) their uncertainty (95% prior interval) cover plausible between-trial standard deviations (Table 17).

**Table 17. Prior Distributions for the Parameters of the MAP Model Used to Derive the Prior for the Single-Agent Sasanlimab Model Parameters**

Parameter	Prior Distribution
$\mu_{1p}$	N (mean = 0, sd = 2)
$\mu_{2p}$	N (mean = 0, sd=1)
$t_{1p}$	log-normal (mean = log (0.25), sd = log (2)/1.96)
$t_{2p}$	log-normal (mean = log (0.125), sd = log (2)/1.96)
$r_p$	Uniform (-1,1)

N=normally distributed; sd=standard deviation.

### Prior Distribution for the Interaction Parameters

Normal priors for the log-odds multipliers  $\eta_{12}, \eta_{13}, \eta_{23}, \eta_{123}$  are used. The prior for  $\eta_{12}, \eta_{13}, \eta_{23}, \eta_{123}$  are specified as percentiles of increase in the odds of DLT due to possible interaction in combination therapy at reference doses;

$\eta_{12}$  is normally distributed, with mean -0.198 and standard deviation 0.101 (corresponds to 20% decrease in DLT odds at median and no increase in DLTs at 97.5th percentile)

$\eta_{13}$  is normally distributed, with mean 0 and standard deviation 0.467 (corresponds to no increase in DLT odds at median and 2.5-fold increase in DLTs at 97.5th percentile)

$\eta_{23}$  is normally distributed, with mean 0 and standard deviation 0.467 (corresponds to no increase in DLT odds at median and 2.5-fold increase in DLTs at 97.5th percentile)

$\eta_{123}$  is normally distributed, with mean 0 and standard deviation 0.354 (corresponds to no increase in DLT odds at median and 2-fold increase in DLTs at 97.5th percentile).

$\eta_{12}$ : 2-way interaction between encorafenib and binimetinib;

$\eta_{13}$ : 2-way interaction between encorafenib and sasanlimab;

$\eta_{23}$ : 2-way interaction between binimetinib and sasanlimab;

$\eta_{123}$ : 3-way interaction among encorafenib, binimetinib, and sasanlimab.

### Summary of Prior Distributions

The prior distributions of the model parameters are provided in Table 18.

**Table 18. Prior Distribution for the Model Parameters**

Parameter	Mean	Standard Deviations	Correlation
Encorafenib single agent parameters: BVN MAP Prior			
$(\log(\alpha_1), \log(\beta_1))$	-0.904, 0.268	0.822, 0.630	0.117
Binimetinib single agent parameters: BVN MAP Prior			
$(\log(\alpha_2), \log(\beta_2))$	-2.785, 0.376	0.596, 0.860	-0.330
Sasanlimab single agent parameters: BVN MAP Prior			
$(\log(\alpha_3), \log(\beta_3))$	-3.247, -0.0135	1.165, 1.009	0.00001
Interaction parameters: Normal prior			
$\eta_{12}$	-0.198	0.101	
$\eta_{13}$	0	0.467	
$\eta_{23}$	0	0.467	
$\eta_{123}$	0	0.354	

$\eta_{12}$ : 2-way interaction between encorafenib and binimetinib;

$\eta_{13}$ : 2-way interaction between encorafenib and sasanlimab;

$\eta_{23}$ : 2-way interaction between binimetinib and sasanlimab;

$\eta_{123}$ : 3-way interaction between encorafenib and binimetinib and sasanlimab.

From Table 19, encorafenib = 300 mg (QD), binimetinib = 45 mg (BID), and sasanlimab = 300 mg once per cycle is an acceptable starting dose for this triple combination.

**Table 19. Summary of Prior Distribution of DLT Rates for the Triplet Combination of Encorafenib in Combination with Binimetinib and Sasanlimab**

Encorafenib (mg QD)	Binimetinib (mg BID)	Prior probabilities that DLT rate is in the interval:			Mean	SD	Quantiles		
		[0, 0.16)	[0.16, 0.33)	[0.33,1]			2.5%	50%	97.5%
300	30	0.5815	0.3482	0.0704	0.1645	0.101	0.039	0.141	0.424
300	45	0.5176	0.3723	0.1101	0.1829	0.116	0.039	0.155	0.479
450	30	0.4429	0.4072	0.1499	0.2037	0.124	0.043	0.176	0.515
450	45	0.4246	0.3840	0.1915	0.2172	0.141	0.038	0.184	0.570

Sasanlimab dose fixed at 300 mg per cycle.

### **Hypothetical On-Study Data Scenarios**

To illustrate the performance of the Bayesian model used to guide dose finding, hypothetical dose finding scenarios following the provisional dose levels specified in the protocol are displayed. In each case, the possible recommended dose that can be used in the next cohort of participants is shown. These recommended doses are determined using the model-based assessment of the risk of DLT in future participants, EWOC criteria and maximum amount of escalation allows (100% of current dose). In practice, the dose recommended by the proposed model may be regarded as guidance. The final recommendation will be based on overall safety profile and PK data.

Table 20 shows data scenarios for the triplet combination and the corresponding recommendations for the next dose.

**Table 20. Next Dose Recommendation and the Interval probability of Target Toxicity and Overdosing at Next Dose**

Scenario	Dose Tested (first 2 dose cohorts)			D/N*	Next Dose options			Pr(TT) at ND	Pr(OD) at ND
	Enco (mg QD)	Bini (mg BID)	Sasanlimab (mg once per cycle)		Enco (mg QD)	Bini (mg BID)	Sasanlimab (mg once per cycle)		
1	300	45	300	0/3	450	45	300	0.462	0.124
	450	45	300	1/3	300	45	300	0.409	0.047
2	300	45	300	1/3	450	45	300	0.449	0.137
	300	45	300	0/3	300	45	300	0.420	0.056
3	300	45	300	2/3	300	45	300	0.544	0.199
	300	30	300	0/3	300	30	300	0.541	0.110
4	300	45	300	1/3	300	45	300	0.538	0.177
	300	45	300	1/3	300	30	300	0.542	0.105
5	300	45	300	2/3	300	30	300	0.597	0.211
	300	30	300	1/4					

**Table 20. Next Dose Recommendation and the Interval probability of Target Toxicity and Overdosing at Next Dose**

Scenario	Dose Tested (first 2 dose cohorts)			D/N*	Next Dose options			Pr(TT) at ND	Pr(OD) at ND
	Enco (mg QD)	Bini (mg BID)	Sasanlimab (mg once per cycle)		Enco (mg QD)	Bini (mg BID)	Sasanlimab (mg once per cycle)		

### Operating Characteristics

A simulation study is used to illustrate the properties of the dose finding model guided by BLRM. Several example scenarios were investigated and each scenario 1000 trials were simulated, with results summarized below.

### Simulation Scenarios

Several scenarios are considered for the triplet (Table 21). Scenario 1 represents the case when the distribution of DLT coincides with prior, ie, the true DLT probability equals to mean of prior DLT. Scenario 2 represents an over and under dosing. Scenario 3 represents under dosing and target dosing.

**Table 21. Combination A: Dose Limiting Toxicity Rate Scenarios (Fixed Sasanlimab Dose 300 mg Once Per Cycle)**

Encorafenib (mg; QD)	Binimetinib (mg; BID)			
	30	45	30	45
	Scenario 1. Prior Means		Scenario 2. Under-Dose and Over-Dose	
300	0.164	0.183	0.100	0.183
450	0.204	0.217	0.297	0.484
	Scenario 2. Under-Dose and Target Dose			
300	0.10	0.12		
450	0.201	0.297		

### Simulation Details

Simulations were performed using R version 3.6.1 (The R-project for Statistical Computing. <https://www.r-project.org/>), and JAGS 4.0 to perform the Markov Chain Monte Carlo (MCMC) analyses.

For each scenario, data for 1000 trials were generated, with a cohort size of 3. At any time during the course of dose finding, escalation to doses where the risk of overdose exceeds 25% is not permitted. The ‘next dose recommendation’ is the dose with maximum probability of overdose among all dose levels that meet the EWOC criteria.

A simulation of dose-escalation is performed using the starting dose of sasanlimab 300 mg, binimetinib 45 mg, and encorafenib 300 mg. CMEK162X2110 doublet data is considered in this exercise. The maximum number of participants per trial was set to 30. Each trial was stopped when the following criteria were met:

- At least 6 participants have been treated at the recommended MTD  $\tilde{d}$ .
- The dose  $\tilde{d}$  satisfies 1 of the following conditions:
- The probability of target toxicity at dose  $\tilde{d}$  exceeds 50%, ie,  $\Pr(0.16 \leq \pi_{\tilde{d}} < 0.33) \geq 50\%$ ;
- A minimum of 12 participants have been treated in the trial.

The following metrics were assessed in the simulations:

- Percentage of participants receiving dose combination(s) in the target toxicity interval;
- Percentage of participants receiving an overdose;
- Percentage of participants receiving an under dose;
- Probability that recommended MTD at the end of the trial is in the target toxicity interval;
- Probability that recommended MTD is an overdose;
- Probability that recommended MTD is an under dose;
- Percentage of trials stopped without MTD declaration;
- Average sample size.

### Simulation Results

Operating characteristics for triplet dose escalation are presented in Table 22. The percentage of trials with a correctly identified MTD ranges from 92.1% to 96.1%. The average sample size was approximately 9 participants for all scenarios.

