## 12.4. Study Design for Sub-Study A

See [Section 4.1](#) for the overall study design in the master protocol.

[figure not shown]
Sub-Study A will start with a Phase 1b safety part with 3 available dose levels (see [Table 7](#)). The enrollment criteria for Phase 1b includes participants with BRAFV600-mutated NSCLC in any line of therapy. Approximately 9-18 participants will be enrolled in Phase 1b, starting with dose level 0 ([Table 7](#) and [Figure 2](#)).

Guidance for Phase 1b dosing (dose level to be evaluated in the next cohort) and enrollment (number of participants to be enrolled in the next cohort) decisions will be based on a

Bayesian Logistic Regression Model (BLRM). The BLRM incorporates single-agent and available combination DLT data (historical and prospectively across dose cohorts) to estimate the posterior probability of under-dosing, target dosing and overdosing, thereby reducing participant risk and increasing efficiency and precision during dose finding with combination treatments.

Phase 2 will begin once the combination RP2D from the Phase 1b is selected. Approximately 62 participants will be enrolled into the Phase 2 part to assess durable OR and participant safety.

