**Figure 2. Sub-Study A Design**

#### 12.4.1. Phase 1b Design

The sasanlimab dose will remain fixed for all dosing cohorts in the Phase 1b part of Sub-Study A.

Beginning with the starting dose level, cohorts of 3-6 participants will be enrolled, treated, and monitored during the 28-day DLT evaluation period (Cycle 1). Participants without DLTs who receive less than 75% of the planned dose of the study intervention in Cycle 1 for reasons other than treatment-related toxicity are not evaluable for DLT. A minimum of 3 DLT-evaluable participants will be required; additional participants will be enrolled in the specific enrollment cohort to replace participants who are not considered DLT-evaluable,

where required. When all DLT-evaluable participants treated in a given enrollment cohort have completed the DLT observation period or experienced a DLT, whichever occurs first, the posterior distribution for the risk of DLT for new participants at different dose levels for the combination of interest will be evaluated. The posterior distributions will be summarized to provide the posterior probability that the risk of DLT lies within the intervals shown below:

- Underdosing: [0, 0.16);
- Target toxicity: [0.16, 0.33);
- Excessive toxicity: [0.33, 1].

In addition to accumulating safety data and observed DLTs, decisions on further participant enrollment and dose level selection will be guided by the escalation with overdose control (EWOC) criterion. A combination dose may only be used for newly enrolled participants if the risk of excessive toxicity at that combination dose is less than 25% (0.25). Refer to [Section 12.10.6](#) for further details of the BLRM.

An RP2D below the MTD, or highest safe dose tested, may be determined based on other safety, clinical activity, PK, and pharmacodynamic data. Before expanding into Phase 2, safety will be confirmed in at least 9 DLT-evaluable participants treated at the RP2D for each combination.

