**Table 22. Combination A: Operating Characteristics**

Scenarios	Participant allocation (%)			Pr (declare MTD) (%)			% stop (no MTD)	Average sample size
	TT	OD	UD	TT	OD	UD		
Prior means	100	0	0	92.1	0	0	8.0	8.5
With under dose and overdose	81.1	18.9	0	92.1	0	0	8.0	8.5

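### The Sub-Study A operating characteristics in Table 22 cannot be obtained from the stated simulation rules, and those rules are not the protocol's own dose-finding design

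*Protocol*

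**What the plan says.** Section 12.10.6 supports the Bayesian logistic regression model (BLRM) with a simulation. It says that for "each scenario 1000 trials were simulated, with results summarized below". The rules, under Simulation Details, are:

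- Cohorts of 3, starting at 300/45 (encorafenib mg QD / binimetinib mg BID).
- No dose with more than a 25% risk of overdose. Among admissible doses, the next is the one with the highest overdose probability.
- Stopping needs at least 6 participants at the recommended MTD and either Pr(target toxicity) of at least 50% or this alternative: "A minimum of 12 participants have been treated in the trial".
- "The maximum number of participants per trial was set to 30".

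Simulation Results then states "The percentage of trials with a correctly identified MTD ranges from 92.1% to 96.1" (per cent) and "The average sample size was approximately 9 participants for all scenarios". Table 22 gives over-dose and under-dose MTD rates of 0 in all three rows, no-MTD rates of 8.0, 8.0 and 3.9%, and mean sizes of 8.5, 8.5 and 8.8.

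The design itself is described elsewhere. Section 12.4 says "Sub-Study A will start with a Phase 1b safety part with 3 available dose levels". Table 7 lists these as 300/30, 300/45 and 450/45. Section 12.4.6 makes a dose a candidate MTD only if at least 6 were treated, Pr(target) exceeds 50% and Pr(overdose) is below 25%, all three together. Sections 12.4 and 12.9.1.3.1 plan about 9 to 18 participants.

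**The concern.** Table 22 tells a reader that the design never declares an over-toxic MTD and needs about 9 participants. Table 20, in the same section, shows the model keeping the highest dose open after one DLT in three. With a true DLT rate of 0.484 at that dose, some trials must end there. If the printed zeros are wrong, the reported operating characteristics understate the chance of carrying an over-toxic dose forward to the 62 Phase 2 participants. A second question is whether the simulated procedure is the one that will be run.

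**Working it through.** **Inputs.** True DLT rates from Table 21, in the order 300/30, 300/45, 450/30, 450/45:

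- Scenario 1 (prior means): 0.164, 0.183, 0.204, 0.217
- Scenario 2 (under- and over-dose): 0.100, 0.183, 0.297, 0.484
- Scenario 3 (under- and target dose, also labelled Scenario 2 in the table): 0.10, 0.12, 0.201, 0.297

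The target interval is [0.16, 0.33). The prior Pr(overdose) at 450/45 is 0.1915 (Table 19). In Table 20 scenario 1 (0/3 at 300/45, then 1/3 at 450/45), 450/45 is still listed, with Pr(overdose) 0.124.

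**1. What would produce the printed rows.** Suppose a trial stops after 3 participants if at least 2 have a DLT, and otherwise always treats 9.

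- P(≥2/3) = 3 × 0.183² × 0.817 + 0.183³ = 8.8% (printed no-MTD rate 8.0%). At 0.12 it is 4.0% (printed 3.9%).
- Mean size = 3 × 0.080 + 9 × 0.920 = 8.52 (printed 8.5). In scenario 3, 3 × 0.039 + 9 × 0.961 = 8.77 (printed 8.8).
- One 450/45 cohort after 0/3: 0.545 × 3 / 8.5 = 19% (printed over-dose allocation 18.9%).

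So the rows resemble a fixed short path. Simulation Details states no such path.

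**2. Scenario 2 under the stated rules.**

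- P(0/3 at 300/45) = 0.817³ = 0.545. 450/45 was admissible a priori, remains so, and has the highest overdose probability, so it is chosen.
- P(≤1/3 at 450/45) = 0.516³ + 3 × 0.484 × 0.516² = 0.137 + 0.387 = 0.524. Table 20 keeps the dose open after 1/3, and 0/3 is more favourable.
- Second cohort at 450/45: 0.545 × 0.524 = 28.6% of trials at least.
- Paths ending at 2/6 there: 0/3 then 2/3 gives 0.137 × 0.363 = 0.050; 1/3 then 1/3 gives 0.387² = 0.149. Together 0.545 × 0.199 = 10.9%. The rebuilt posterior at that point has Pr(target) 0.545 and Pr(overdose) 0.152, so the trial stops with 450/45 as MTD.
- No such MTD in 1000 trials: 0.891¹⁰⁰⁰, about 10⁻⁵⁰.

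**3. Rebuilt model.** Table 18 priors, the stated interaction model, and the doublet data at weight 1/(1 + 2 × 0.25²/2² × 44) = 0.421. The doublet split by dose is not in the protocol. It was calibrated (best fit: 1 DLT in 44) and matches Table 19 interval probabilities and means within 0.004 and Table 20 within 0.011. Each variant used 1000 to 4000 trials.

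| Rules | Scenario | Correct | Over-dose MTD | Under-dose MTD | No MTD | Mean N |
|---|---|---|---|---|---|---|
| Simulation Details, four-dose grid | 1 | 94% | 0% | 0% | 6% | 11.8 |
| same | 2 | 42–44% | 38–39% | 7% | 11% | 13.5 |
| same | 3 | 84–85% | 0% | 12% | 3% | 12.5 |

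With the Table 7 levels, the Section 12.4.6 criteria and a cap of 18, scenario 1 gives 75% correct and 26% without an MTD; scenario 2 gives 51% correct and 32% over-dose MTD; scenario 3 gives 67% correct and 22% under-dose MTD. Across all variants (grid, selection by overdose or target probability, cap, early stop), the scenario 2 over-dose MTD rate is 10% to 39%, and mean N is never below 9.8.

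**4. Scenario 3 and sample size.** After 0/6 or 1/6 at 450/45, the rebuilt Pr(target) is 0.20 or 0.40, so a trial cannot stop at 9. On the Table 7 levels, 1/3 then 1/3 at 300/45 has probability (3 × 0.12 × 0.88²)² = 7.8%. Table 20 scenario 4 then lists 300/45 with Pr(target) 0.538 and no longer lists 450/45, which gives an under-dose MTD if 450/45 was also closed after the first 1/3 (borderline in the rebuild, Pr(overdose) about 0.25).

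**5. What the zeros show.** In scenarios 1 and 3 no dose exceeds 0.33, so 0% over-dose MTD holds by construction. In scenario 1 all four doses lie in the target interval, so the percentage correct is only 100% minus the no-MTD rate.

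**6. Simulated against planned design.**

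| | Simulated | Protocol |
|---|---|---|
| Dose grid | four, including 450/30 (Table 21) | three, without 450/30 (Table 7) |
| MTD | allowed at N ≥ 12 without Pr(target) ≥ 50% | Pr(target) > 50% required (12.4.6) |
| Size | up to 30 | about 9–18 (12.4, 12.9.1.3.1) |

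**The case against.** A reader might infer more than the documents support.

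- **That Table 22 is arithmetically impossible**, because 92.1 + 8.0 = 100.1 with 1000 trials. A 0.1-point excess is a reporting slip, and step 1 shows that a fixed path comes close to the printed figures.
- **That the matching MTD and sample-size results in the first two rows prove an error.** The starting dose 300/45 has rate 0.183 in both scenarios, and the allocation columns differ.
- **That the rows for scenarios 2 and 3 contradict each other.** They need not on the four-dose grid, where 450/30 is in target in both.
- **That 0% under-dose allocation in scenario 2 conflicts with Table 20.** The 300/30 cohort after 2/3 DLTs in Table 20 is hypothetical input, not a model recommendation.
- **That the overdose-control rule or the model is discredited.** Tables 19 and 20 reproduce, every dose stays subject to the 25% limit, and the protocol calls the model guidance.

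It is also fair to say that the simulation is described as illustrative, that 18 is an estimate, that Section 12.4.6 defines only a potential candidate, and that Section 12.4.1 adds a later safeguard: "safety will be confirmed in at least 9 DLT-evaluable participants treated at the RP2D for each combination". Leaving that confirmation out does not make an MTD simulation wrong. The scenario 1 rebuild (94% correct, 6% without an MTD) is close to print.

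None of this rescues the 0% over-dose MTD in scenario 2, the 0% under-dose MTD in scenario 3 or the mean size of about 9. If an unstated early-stopping rule was coded, the protocol needs to say so. Adding a stop after at least 2/3 DLTs in the first cohort still left over-dose MTDs at 10% or more in the rebuild.

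**Conclusion.** The concern holds as a fault in Table 22 and its summary sentence. In the one scenario able to test it, the stated rules give an over-toxic MTD in roughly 10% to 39% of trials, not 0%. The 28.6% figure needs only the protocol's own tables and rules. The 10.9% figure also uses the rebuilt posterior at 2/6, and the 10% to 39% range rests on doublet DLT data by dose that are assumed and calibrated to Tables 19 and 20. Individual percentages should therefore be read as approximate. Separately, the simulated grid, MTD rule and cap are not those of the protocol, so even a correct run of the stated simulation would not describe the planned design. The overdose-control rule itself is not shown to be faulty.

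**What to change.** Rerun the simulation on the Table 7 levels, with the Section 12.4.6 MTD criteria and the planned sample size, and state the next-dose selection rule and any early-stopping rule that was actually coded. Replace Tables 21 and 22, the 92.1% to 96.1% sentence and the average-size sentence with the results. Say how the allocation percentages are averaged, and correct the duplicate Scenario 2 label in Table 21. Optionally add a scenario in which the starting dose is itself over-toxic. Where the simulated rules and Sections 12.4 to 12.4.6 and 12.9 differ, the sponsor should reconcile the passages; no dosing rule is proposed here.

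The cost is a day or two of statistician time and corrected tables at the next amendment. The stated figures will be less favourable.
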